8.1 Interim analyses

There were no planned interim analyses for this study. However, an analysis was carried before full accrual was completed to reassess some of the assumptions used in the sample size calculations. As a result of this analysis it was observed that the overall proportion of women taking insulin in the study was larger than the one estimated in the original sample size calculations. Based on this information, it was established that a reduced sample of 535 participants would achieve the same 80% power to answer the primary research question. Therefore, the total sample size will be 535.

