plan (SAP) will be provided in a separate document. The SAP document will provide a more technical

1752 and detailed elaboration of the principal features of the planned analyses. The SAP will be finalised
1753 prior to study enrolment, at the latest before any substantial information in the trial has accumulated.
1754

1755 Analyses will be performed using R software.
1756

1757 11.2. Determination of sample size

1758 Our sample size is based on the following; a) 35% of participants will require insulin in the control
1759 arm, based on information from the MiG trial and data from University Hospital Galway and University
1760 Hospital Cork; b) ability to detect a minimum of 33% relative risk reduction in proportion of participants
1761 requiring insulin in the experimental (metformin) group (40% to 28% absolute reduction; in the MiG
1762 trial only 40% of participants on metformin required insulin); c) significance level of 0.05 and 80%
1763 power; d) drop-out rate of 5% or less; and e) non-adherence rate of 8% in metformin group. Based on
1764 these assumptions, we require a total of 550 participants. This sample size will also have 80% power
1765 to demonstrate a difference between the proportions of 12% or more (i.e. a reduction from 60-48%) in
1766 the secondary outcome of excessive GWG.
1767

1768 There are 7,000 deliveries annually in participating sites. From ATLANTIC DIP 1 we have identified a
1769 prevalence of 12.4% for GDM using IADPSG criteria. In our previous universal screening project, we
1770 had a consent rate of 75% but a testing rate of circa 50%. On a second study examining uptake rates
1771 in primary v secondary care, the screening uptake rate was 88% for screening in secondary care.
1772 With prevalence of 12% we would expect to diagnose upto 840 pregnancies with GDM annually. For
1773 the secondary outcome of baseline to post-partum weight change, there is a greater concern with loss
1774 to follow-up, as post-pregnancy follow-up rates have been reported in some studies to be less than
1775 70%. For this outcome, even with a loss-to follow-up of 50% the resulting 138 per arm will have 80%
1776 power, at the 0.05 significance level, to detect a minimum difference in mean weight change of
1777 1.36kgs (assuming a standard deviation of the change in weight of 4kgs). However, every effort will
1778 be made to achieve follow-up rates of >95% for post-partum follow-up, and we will implement a

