5.2 Study endpoints

5.2.1 Primary endpoint

A composite primary outcome of insulin initiation or fasting hyperglycemia (glucose ≥ 5.1 mmol/l) on study specific fasting laboratory glucose at gestational weeks 32 or 38 will be used. This approach allows us to measure 'treatment failure' in two discreet ways. The introduction of insulin reflects clinically meaningful hyperglycaemia, and is measured at any time during clinical trial. In addition, a standardised fasting glucose will be completed at gestational weeks 32 and 38, to capture additional participants who have fasting hyperglycaemia but have not had insulin introduced during the clinical trial.

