6.3 Randomisation and Blinding

Participants will be randomly assigned to receive either metformin or placebo in a 1:1 ratio. Random permuted blocks will be used to ensure similar numbers of participants in each intervention arm throughout the trial and equal numbers in each arm by the end of the study. A minimisation strategy will be used; allowing equal numbers of women with a BMI $\leq/ > 30$ and a history of GDM to be distributed between groups.

A web-based randomisation system will allow participating sites to login and obtain allocated treatment numbers and participant IDs after confirming eligibility through inclusion and exclusion criteria. The treatment number will correspond to a treatment kit at the site. This centralised system will ensure allocation concealment; preventing trial staff from knowing which treatment group will be allocated. Blocks of varying length will also be used to reduce the predictability of the allocation sequence

This trial will be conducted in a double-blind fashion with a placebo control identical to metformin tablets to avoid bias in assessing outcomes. Site Investigators, site personnel, participants, and outcome assessors will be blinded to treatment allocation.

In the case of an emergency, when knowledge of the participants's study treatment assignment is essential for the clinical management of the participant, an investigator may un-blind a participant. Any intentional or unintentional breaking of the blind will be recorded and reported to the sponsor as soon as possible.

7 Sample Size

Our sample size for testing this hypothesis is based on the following; a) 35% of women will require insulin in the control arm, based on information from the MiG trial and data from University Hospital Galway and University Hospital Cork; b) ability to detect a minimum of 33% relative risk reduction in the proportion of women requiring insulin in the experimental (metformin) group (40% to 28% absolute reduction; in the MiG trial only 40% of women on metformin required insulin); c) significance level of 0.05 and 80% power; d) drop-out rate of 5% or less; and e) non-adherence rate of 8% in metformin group. Based on these assumptions, we require a total of 550 participants. This sample size will also have 80% power to demonstrate a difference between the proportions of 12% or more (i.e. a reduction from 60-48%) in the secondary outcome of excessive GWG.

EMERGE NUIG-2016-01, Statistical Analysis Plan Version 1, 21/03/2023

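### The 80% power stated at 550 and at 535 rests on insulin use, and no rate, effect or power is derived for the composite primary outcome

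*SAP*

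**What the plan says.** **Outcome.** SAP 5.2.1 declares "A composite primary outcome of insulin initiation or fasting hyperglycemia", judged on study-specific glucose at week 32 or 38. It says the glucose part is there "to capture additional participants who have fasting hyperglycaemia but have not had insulin introduced during the clinical trial". Protocol 7.3.1 and SAP 8.2 and 13.1 define the same composite.

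**Sample size.** Protocol 11.2 opens with "Our sample size is based on the following; a) 35% of participants will require insulin in the control" arm, and SAP 7 repeats that "35% of women will require insulin in the control arm". The effect is the "ability to detect a minimum of 33% relative risk reduction in the proportion of women requiring insulin in the experimental (metformin) group", glossed in the same sentence as 40% to 28%. Both texts add alpha 0.05, 80% power, at most 5% drop-out and 8% non-adherence on metformin, and arrive at 550.

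**Re-estimation.** SAP 8.1 reports that "the overall proportion of women taking insulin in the study was larger than the one estimated in the original sample size calculations", and concludes that "a reduced sample of 535 participants would achieve the same 80% power to answer the primary research question". It gives neither the observed proportion nor the effect size used.

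**Primary analysis.** The Protocol synopsis describes a comparison of the composite. Protocol 11.5 and SAP 13.1 describe a comparison of the proportion needing insulin. In SAP 13.1 this comes shortly after the composite is defined.

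**The concern.** The glucose component adds events by design: it counts women who never start insulin. It therefore raises the event rate in both arms. What it does to the difference between arms depends on how common these events are and how far metformin prevents them, and the plan states neither. Power for insulin initiation does not carry over to the composite without those two quantities.

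The number matters because SAP 8.1 uses it to justify a smaller target, and because a null result on the composite could be reported as coming from a trial with 80% power for that outcome. The insulin-only wording in Protocol 11.5 and SAP 13.1 adds to the difficulty, since a reader cannot tell which variable the 80% is meant to serve.

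**Working it through.** **Step 1. Reproduce 550 (Protocol 11.2, SAP 7).** Two proportions, pooled variance under the null, 1:1, alpha 0.05 (sidedness is not stated; two-sided assumed), 80% power:

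n per arm = [1.96·√(2p̄(1−p̄)) + 0.84·√(p1(1−p1) + p2(1−p2))]² / (p1−p2)²

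- 40% v 28%: n = 244. Dividing by 0.95 × 0.92 gives 280 per arm, total 560. Dividing by 0.87 gives 281 per arm, total 562. With a continuity correction n = 260, and 520/0.95 gives 548.
- 35% with a 33% relative reduction (23.45%): n = 243, giving 558, 560 and 548 on the same three routes.

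So 550 is reached within about 3% from insulin rates alone, with no glucose-event rate. The two rate pairs disagree (40% to 28% is a 30% relative reduction, not 33%), but the result holds for either.

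**Step 2. Try 535 (SAP 8.1).** The observed proportion is missing, so 535 cannot be reproduced. It is compatible with a control insulin rate of about 41% at a fixed 30% relative reduction: 41% v 28.7% needs 235 per arm, and 235/(0.95 × 0.92) gives 269 per arm, total 538. Holding the 12-point difference instead moves the total the other way: 41% v 29% needs 566.

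**Step 3. Illustrate the composite at 535.** The documents give no glucose-event rate, so these are assumptions: insulin in 40% v 28%; a fraction q of non-insulin control women meet the glucose criterion; the fraction on metformin is r·q. Then:

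- control composite = 0.40 + 0.60q
- metformin composite = 0.28 + 0.72·r·q
- power = Φ{ [|p1−p2|·√n − 1.96·√(2p̄(1−p̄))] / √(p1(1−p1) + p2(1−p2)) }

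With 5% loss, n = 535 × 0.95 / 2 = 254.1 per arm. Example for q = 10%, r = 1: rates 46.0% v 35.2%, and Φ[(0.108 × 15.94 − 1.361)/0.690] = Φ(0.52) = 70%.

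| Effect on glucose-only events | q = 10% | q = 20% | q = 30% |
|---|---|---|---|
| None (r = 1) | 46.0 v 35.2: 70% | 52.0 v 42.4: 58% | 58.0 v 49.6: 48% |
| 15% relative reduction (r = 0.85) | 78% | 76% | 75% |
| 30% relative reduction (r = 0.70) | 85% | 89% | 92% |

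Insulin-only power on the same basis is 82%.

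**Step 4. Vary the inputs.**

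- *Loss.* Counting the 8% non-adherence as further loss (13% in all, 232.7 per arm), insulin-only power is 78%. The no-effect row becomes 66%, 55% and 44%, and the 30% row 82%, 86% and 90%.
- *Other rate pair.* With 35% v 23.45%, 5% loss and no effect: 68%, 56% and 45%.
- *Higher insulin rate* (the direction SAP 8.1 reports), 30% relative reduction, 5% loss. At 45% in controls, insulin-only power is 88% and the no-effect row is 79%, 68% and 58%. At 50% these are 93%, and 86%, 78% and 68%.

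**Step 5. Detectable difference.** At 535, for a control composite rate of 46% to 58%, 80% power corresponds to 12.1 to 12.4 percentage points with 5% loss, or 12.7 to 13.0 points with 13% loss.

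**The case against.** The strongest reply has four parts.

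1. SAP 8.1 does attach a power figure to the primary question, so it would be wrong to say that none is stated. This stands. What is missing is any basis for that figure in composite terms. For 535, the reliance on insulin is read from the only evidence SAP 8.1 cites, because the working is not shown.

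2. Protocol 11.5 and SAP 13.1 word the primary analysis as insulin need, and the power would fit that analysis. This is true of the wording. It does not settle the matter: the outcome definitions in both documents, and the synopsis description of the analysis, are the composite. The passages need reconciling, and until that is done the match cannot be relied on.

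3. A reader might infer from the lower rows of power that the trial is underpowered, or take 48% to 92% as limits on its true power. The documents support neither. The event fractions and effects are chosen, not observed; one variant in step 4 already falls below 48%. A higher insulin rate at a fixed relative reduction raises power, in one case above 80% even with no effect on glucose-only events.

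4. The practical effect is small. The cut is 15 women (2.7%), which at 40% v 28% with 5% loss lowers insulin-only power from 82.7% to 81.7%, and the first no-effect composite value from 71.1% to 69.9%. Restating power changes no estimate or test, and the confidence interval will show what a null result excludes. This also stands: the point concerns what the plan may claim, and the size of the cut is secondary.

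**Conclusion.** The point holds as a mismatch between the declared outcome and the basis of the stated power. The 80% at 550 is derived from insulin requirement alone. The 80% at 535 is claimed for the primary question on the evidence of insulin use alone, without the observed rate or effect. Neither is supported for the composite. There is no arithmetic error in 550, which reproduces within about 3%.

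Composite power could lie on either side of 80%. It depends on how common glucose-only events are, how far metformin reduces them, the actual insulin rate, and how non-adherence is treated. At 40% v 28% with 5% loss, even a 15% relative reduction in glucose-only events leaves power at 75% to 78%, so the 80% cannot be assumed to carry over. All composite figures rest on assumed rates and a two-sided test.

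**What to change.** - In SAP 7 and 8.1, label the 80% as power for insulin initiation only.
- In SAP 8.1, give the observed pooled insulin rate, and the effect size, loss and non-adherence assumptions that led to 535.
- Add the composite power at 535, or the difference detectable with 80% power, based on the pooled composite rate. Calculate it on blinded data, before the randomisation codes are used for the analysis in SAP 8.2. State the assumptions with it.
- Word the primary analysis in Protocol 11.5 and SAP 13.1 as a comparison of the composite, in line with the synopsis and the outcome definitions.

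No extra enrolment is proposed. The cost is one recalculation and changes of wording, with any Protocol change following the approval route in Protocol 15.7. The stated power may turn out less favourable than 80%.

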8.2 Final analyses

An analysis of the primary outcome of insulin initiation or hyperglycaemia and the secondary perinatal (maternal and infant) outcomes will be performed after the last participant has given birth but before the database lock, to initiate dissemination of key results. This analysis, which requires the randomization codes, will be carried out by an independent statistician, to maintain the blind among the relevant members of the statistics and data management team and other potential outcomes assessors. All other analyses identified in this SAP will be performed after the last participant has completed the study. Before carrying out the final analyses, the data management team are responsible for the database cleaning process to ensure the integrity of the analyses. No database will be locked until the SAP has been approved. Key statistics and study results will be made available following database lock and before completion of the final CSR.

Any post-hoc exploratory analyses completed to support planned study analyses, which were not identified in this SAP, will be documented and reported in appendices to the CSR.

9 ***Analysis populations***

9.1 Intention-to-Treat Analysis Set

The intention-to-treat (ITT) analysis set, also termed full analysis set in the International Conference on Harmonization (ICH) E9 guideline, will include all randomised participants regardless of what study medication they received. The primary and secondary analyses will be performed on an ITT basis.

9.2 Per-protocol

This set will exclude the subset of participants in the Intention-to-treat analysis set who are non-compliant with the protocol, including errors in treatment assignment, violation of inclusion/exclusion criteria, major protocol deviations and poor adherence with study medication (defined as less than 80% overall adherence). A per-protocol analysis will supplement the ITT analysis as a secondary analysis.

9.3 Safety Analysis Set

The safety analysis set will include all randomised participants who received at least one dose of study medication. This set will be considered for the analysis of all the safety outcomes.

10 ***General issues for Statistical Analysis***

10.1 Software used for the analysis

All primary and secondary statistical analyses will be validated by an independent statistician, or using independent software (R, SAS, SPSS, Minitab or Stata). All of the code generated will be kept by both the study statistician and the independent statistician.

10.2 Methods for Withdrawals, Missing Data, and Outliers

An analysis of missing data for secondary analyses will be carried out to identify the likely missing data mechanism (e.g. missing completely at random, missing at random, and missing not at random). A suitable multiple imputation strategy will be employed (if deemed appropriate) to determine the sensitivity of missing data on the inference gleaned from the final model.

10.3 Data Transformations

Due to the nature of the primary and secondary endpoints analysis, it is not expected that any of the data will have to be transformed.

10.4 Multicentre Studies

This is a two-center clinical study, with standardization of participant enrolment, data entry and adverse event reporting. Investigational sites will follow the requirements of a common protocol, data collection procedures and forms.

Given the nature of the intervention, women from the two centers are considered exchangeable. Demographic and baseline data will be presented by each centre in the CSR to explore differences in patient characteristics between the centers.

10.5 Multiple Testing

Since the primary analysis for performance is based only on one endpoint (i.e. the reduction of the effects of Gestational Diabetes Mellitus in pregnant women), no multiple comparisons will be necessary.

10.6 Planned Subgroups, Interactions, and Covariates

Variation of treatment effects for primary outcome induced by baseline/demographic variables will be explored using interaction analysis. Relevant variables will be race (Caucasian vs non-caucasian), age (<30 years vs \geq 30 years), previous GDM (Yes/No) and whether this is the participant's first pregnancy.

11 Study Subjects

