811 is up to 28 weeks (+6 days) gestation, which can occur on the same day as screening or up to 7 days
812 post-screening.
813

814 Participants at all trial sites will also be invited to partake in a bio-banking sub-study which involves
815 obtaining maternal blood samples at randomisation and gestational age 38 weeks (+/- 1 week) and
816 also a cord blood sample at delivery. This is executed under a separate Ethics Committee approved
817 protocol and is executed as guided by local practice patterns and the availability of resources
818 (including staff).
819

820 Once the participant has been randomised, additional data collected will include:
821

822 1. Physical measurements and vital signs (heart rate, BP, height, weight)
823 2. Demographics (date of birth (DOB), race)

824 3. Social history (smoking and alcohol)
825 4. Socioeconomic status
826 5. Baseline gastrointestinal symptoms
827 6. EQ5D-5L Questionnaire
828 7. Laboratory tests (see section 8.4.5)
829 8. Medical resources used since diagnosis of pregnancy
830 9. Usual care received

831
832 The participant will then be dispensed study medication and administration instructions. The pack
833 numbers of dispensed medication will be documented on the dispensation log.

834
835 **8.3.2. Prenatal Visit and Procedures**

836
837 Prenatal visits will occur approximately every 2 weeks post randomisation in line with routine
838 antenatal clinic visits. Visits that do not require an in person physical measurement, laboratory
839 assessment or drug dispensation can be completed over the telephone. The following data will be
840 collected and procedures will be performed:

841
842 1. Gestational age in weeks
843 2. Review of concomitant medications
844 3. Review of insulin requirements
845 4. Review of adverse events
846 5. Gastrointestinal symptom review
847 6. Review of hypoglycaemic events
848 7. Review of medical resources used
849 8. Glucometer data download (at in person visits only, see section 8.4.7.)

850
851 The following data will be collected in addition to the above:

852
853 1. Study drug dispensing (every 4 weeks)
854 2. Physical measurements and vital signs (heart rate, BP and weight to be taken at gestational
855 weeks 32 (+/- 1 week) and 38 (+/- 1 week))
856 3. Usual care received (week 4)
857 4. Laboratory tests (at gestational week 32 (+/- 1 week) AND at gestational week 38 (+/- 1
858 week), see section 8.4.5.)

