6.2 General Study Population

The population for the trial is pregnant women between the ages of 18-50 years, with a diagnosis of GDM between 24-28 weeks gestation (+ 6 days).

EMERGE NUIG-2016-01, Statistical Analysis Plan Version 1, 21/03/2023

Women diagnosed using a 75g Oral Glucose Tolerance Test (OGTT) and International Association of Diabetes in Pregnancy Study Groups (IADPSG) criteria for diagnosis will be eligible to be enrolled in the study. Eligible women must be resident and intend to deliver within the selected trial sites. They must also fulfil all of the Inclusion criteria and none of the Exclusion criteria of the EMERGE Protocol. The geographical area and study population include women from urban and rural locations and women in public and private health care.

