12.1 Demographics

Age and race (Caucasian vs non-Caucasian) will be considered demographic variables. Mean, standard deviation, median, max and min will be reported for age, and counts and percentages will be reported for race.

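### SAP 10.6 examines age as an effect modifier only through an unexplained split at 30 years; prespecifying a continuous-age interaction as well would be a cheap improvement

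*SAP*

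**What the plan says.** SAP 10.6 sets out the effect-modification analysis: "Variation of treatment effects for primary outcome induced by baseline/demographic variables will be explored using interaction analysis". It names four variables, each with two levels as written: race, age, previous GDM and first pregnancy or not. For age the wording is "Relevant variables will be race (Caucasian vs non-caucasian), age (<30 years vs" 30 or over. No reason is offered for 30, the model is not specified, and neither 10.6 nor any other section adds an interaction with age as a continuous variable.

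Exact age is available. Protocol 8.3.1 lists "Demographics (date of birth (DOB), race" among the data collected after randomisation, and SAP 12.1 treats age as continuous in the baseline description: "Mean, standard deviation, median, max and min will be reported for age". The only age figure in the documents is the eligibility range in SAP 6.2: "The population for the trial is pregnant women between the ages of 18-50 years". There is no expected mean, SD or share under 30, and no power statement for any interaction.

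**The concern.** A single cut treats women aged 18 and 29 as alike, and likewise women aged 30 and 50, while it separates 29 from 30. If the effect of metformin drifts gradually with age, most of that gradient lies within the two groups and the test cannot use it. The loss is smallest when the cut falls at the median and grows as the groups become unequal. Protocol 6.1.2 and SAP 3 name increasing age as a risk factor for GDM, so a minority under 30 is plausible, though the documents do not show it.

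At stake is how informative a null age interaction would be. The trial is sized for its main effect, so interaction tests start with little power, and an unexplained cut can reduce it further.

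**Working it through.** **Inputs from the documents.** Age form: two groups split at 30 (SAP 10.6). Total N: 535 (SAP 8.1, reduced from 550). Rates: "40% to 28% absolute reduction"; error rates: "significance level of 0.05 and 80% power"; attrition: "drop-out rate of 5% or less" (all SAP 7). Allocation 1:1 (SAP 6.3).

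**Assumptions, not in the documents.** A two-sided test; approximately normal age; the share under 30, or the mean and SD of age; the size and shape of the interaction; a logistic model, as in SAP 13.1.

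**Step 1: the plan's own figure.** No figure is stated for the age interaction, so only the primary sample size can be reproduced. For 40% v 28%, two-sided 0.05 and 80% power, the usual two-proportion formula with continuity correction gives 260 per arm, 520 in total. Then 520/0.95 = 548, against 550 stated. Without the correction it gives 244 per arm, and 488/(0.95 × 0.92) = 559 if the 8% non-adherence is treated as further loss. Either is within 3% of 550. The size is thus explained by the main effect alone.

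**Step 2: information kept by the split.** For normal age and a linear interaction, with a share p below the cut, efficiency relative to continuous age is

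eff = φ(z_p)² / [p(1 − p)],

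where z_p is the normal quantile of p and φ the normal density. At p = 0.50: 0.3989²/0.25 = 0.637. At p = 0.20: 0.2800²/0.16 = 0.490.

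**Step 3: power after the split**, when continuous age would have 80%:

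power = Φ[√eff × (1.96 + 0.8416) − 1.96].

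At p = 0.50: Φ(0.798 × 2.8016 − 1.96) = Φ(0.276) = 0.61. At p = 0.20: Φ(0.700 × 2.8016 − 1.96) = Φ(0.001) = 0.50.

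| Share under 30 (assumed) | Efficiency | Information lost | Power, from 80% |
|---|---|---|---|
| 50% | 0.637 | 36% | 61% |
| 30% | 0.576 | 42% | 57% |
| 25% | 0.539 | 46% | 54% |
| 20% | 0.490 | 51% | 50% |
| 15% | 0.426 | 57% | 45% |

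Efficiency is greatest at p = 0.50, so under these assumptions no share under 30 brings the loss below 36%.

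**Step 4: simulation, two shapes.** N = 535, control rate 40%, log odds ratio for metformin −0.54 as the reference treatment effect (40% v 28%), age SD 5, 3,000 runs per setting (Monte Carlo standard error at most √(0.25/3000) = 0.009). The linear shape changes the log odds ratio by 0.52 per SD of age from its value at the mean. The step shape shifts it by 1.1 for women under 30.

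| Mean age | Linear: continuous | Linear: split | Step at 30: continuous | Step at 30: split |
|---|---|---|---|---|
| 30 | 0.76 | 0.56 | 0.68 | 0.87 |
| 32 | 0.77 | 0.54 | 0.67 | 0.85 |
| 33 | 0.77 | 0.51 | 0.57 | 0.79 |
| 34 | 0.78 | 0.45 | 0.46 | 0.71 |
| 35 | 0.78 | 0.38 | 0.37 | 0.63 |

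With no interaction (mean age 33) the rejection rates are 0.054 for continuous age and 0.051 for the split, so type I error does not separate the two.

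**Step 5: smaller linear interactions.** Same design, 1,500 runs per setting, mean age 30 / 33 / 35.

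| Change in log odds ratio per SD | Continuous | Split |
|---|---|---|
| 0.5 | 75 / 75 / 75% | 53 / 48 / 37% |
| 0.3 | 37 / 38 / 37% | 26 / 21 / 17% |
| 0.2 | 19 / 22 / 18% | 13 / 15 / 10% |
| 0.1 | 8 / 8 / 9% | 7 / 7 / 6% |

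For scale, 0.5 per SD is very large. It implies metformin odds ratios of exp(−0.54 − 0.5) = 0.35 one SD below mean age, exp(−0.54) = 0.58 at the mean, exp(−0.54 + 0.5) = 0.96 one SD above and exp(−0.54 + 1.0) = 1.59 two SDs above.

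**The case against.** The strongest reply is that the advantage of continuous age depends on the shape of the interaction, and the documents support no particular shape. If the effect steps at 30, the split is the better test: 0.79 v 0.57 at mean age 33. That stands, and it is why the split should be kept for display and linearity checked. The documents give no reason to expect a step at 30, however.

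Second, interactions large enough for the choice to matter much are extreme. At 0.2 per SD or less, either form misses the interaction about four times in five or more. This also stands: a null result would be weak evidence even with continuous age, because trial size is the main limit.

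Third, the analysis is exploratory, a cut fixed in advance at least prevents a data-driven threshold, and SAP 4 allows further exploratory analyses. This is correct, but SAP 4 also says that analyses not specified in the SAP will be identified as post hoc or unplanned. A continuous-age test added later would carry that label.

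A reader might go further and infer that a null age result would undermine the trial's conclusion about all women with GDM. The documents do not support that. Protocol 6.2 and SAP 3 describe the broad population by BMI and by not waiting for lifestyle measures to fail; they make no age-specific claim. Age as a risk factor for developing GDM is not evidence that age modifies the effect of metformin.

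**Conclusion.** The point holds as a limited improvement. SAP 10.6 reduces an available continuous variable to two groups without a stated reason and plans no continuous-age interaction. If age is roughly normal and the interaction roughly linear on the logit scale, the split loses at least about 36% of the information and about 50% if a fifth of women are under 30, so 80% power becomes about 61% or less.

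It would be tempting to read a fixed loss into this, or to conclude that continuous age is always better. Neither follows: the size depends on an age distribution that the documents do not give, and the direction depends on the shape of the interaction. The consequence is confined to one of four exploratory interaction variables. The primary test, its power and its type I error are unaffected.

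**What to change.** In SAP 10.6, prespecify the treatment-by-age interaction for the primary outcome with age continuous in the logistic model, including the main effect of age. Check linearity on the logit scale with a spline term. Present the fitted treatment effect with its 95% CI across the observed age range. Keep under 30 v 30 and over as a descriptive row in the subgroup display, and give the reason for that cut if there is one.

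The cost is a line or two of SAP text and one further model, with no new data. The downside is the linearity assumption, which the spline check addresses in part. The change should be made before the randomisation codes are used for the primary-outcome analysis described in SAP 8.2; after that point the continuous-age result should be reported as post hoc.
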